7.2. Analysis Methods for Estimands

This is a Phase 2a study. No formal hypothesis will be tested and there will not be a confirmatory treatment comparison.

The following ICEs have been identified for this study (see [Section 3](#)):

1. Early discontinuation from the randomized IP for any reason,
2. Not on stable CFTR modulators for participants on modulators,
3. Use of antibiotics during an acute event that could affect NSP levels.

The table below gives an overview which analysis set(s) and strategy to deal with related ICEs will be used for the Estimands.

Estimand	Analysis Set	Strategy for ICEs
Primary, Secondary, and Exploratory PK	PK Analysis Set	For the first ICE, While-on-Treatment strategy: data collected prior to the occurrence of the ICE, i.e., to discontinuation of IP, will be included in the analysis. For the second and third ICE, the Treatment Policy strategy will be used, i.e., all data will be included in the analysis.
Safety	Safety Analysis Set	For the first ICE, While-on-Treatment strategy: data collected prior to the occurrence of the ICE, i.e., to discontinuation of IP, will be included in the analysis. For the second and third ICE, the Treatment Policy strategy will be used, i.e., all data will be included in the analysis.
Exploratory PD	PD Analysis Set	For the first and the third ICE, While-on-Treatment strategy: data collected prior to the occurrence of the ICE, i.e., to discontinuation of IP or to the use of antibiotics with impact on NSP levels, will be included in the analysis.

		For the second ICE, the Treatment Policy strategy will be used, i.e., all data will be included in the analysis.
Exploratory Efficacy, Microbiology	ITT Analysis Set	For the first ICE, While-on-Treatment strategy: data collected prior to the occurrence of the ICE, i.e., to discontinuation of IP, will be included in the analysis. For the second and third ICE, the Treatment Policy strategy will be used, i.e., all data will be included in the analysis.

The While-on-Treatment strategy will be applied for the first ICE: data collected after discontinuation of IP will be excluded from the derivation of PK parameters and from statistical analysis for PK, safety, PD, and efficacy analysis.

The Treatment Policy strategy will be applied for the second ICE: data will be included in derivation of PK parameters and in the PK analysis irrespective of changes in CFTR modulator use.

For the third ICE which is applicable for PD, Insmmed clinical team will review by participant listings of concomitant medication to judge whether antibiotics have been administered which may invalidate the use of the PD concentrations for the analysis. If this is the case, PD data after the start of such concomitant medication will be excluded from the statistical analysis.

Before DBL, the participants' data will be discussed during a Blind Data Review Meeting (BDRM). It will be decided whether ICEs occurred and up to which timepoint data for the While-On-Treatment strategy will be included in any analysis. The protocol deviation tracker will also be reviewed and discussed during the BDRM. The decisions will be documented in a Data Review Report (meeting minutes). Unblinding after DBL can only occur when the Data Review Report has been agreed upon. This will be documented by email approval. After unblinding, it will be checked if participants received treatment other than the randomized. Furthermore, it will be confirmed that the reasons to exclude participants or data records from an analysis set or analysis, respectively, are still in the same way valid as before unblinding. Any deviations between the pre-DBL and post-DBL data with an impact on decisions made during the BDRM will be documented in the final Data Review Report. If decisions made during the BDRM must be revised this will also be documented in the final Data Review Report and a rationale will be provided for the revision. The Data Review Report will only be finalized and signed after DBL.

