## **7. DISCONTINUATION OF STUDY DRUG AND PARTICIPANT DISCONTINUATION/WITHDRAWAL**

### **7.1. Discontinuation of Study Drug**

Participants who discontinue the study drug for any reason may not continue in the study unless discontinuation was due to an AE. Participants who discontinue the study will be asked to attend an Early Discontinuation Visit and undergo the scheduled assessments (SoA, [Section 1.3](#)).

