## 10.3. Appendix 3: AEs and SAEs: Definitions and Procedures for Recording, Evaluating, Follow-up, and Reporting

### 10.3.1. Definition of AE

AE Definition

An AE is defined as any untoward medical occurrence in a participant or clinical investigation participant administered a pharmaceutical product and which does not necessarily have to have a causal relationship with this treatment. An AE can therefore be any unfavorable and unintended sign (including an abnormal laboratory finding, for example), symptom, or disease temporally associated with the use of a medicinal product, whether or not considered related to the medicinal product (ICH E2A Guideline. Clinical Safety Data Management: Definitions and Standards for Expedited Reporting, October 1994).

A treatment emergent adverse event (TEAE) is defined as any AE that occurs after the first dose of study IMP and within 28 days after the last dose of study IMP

Definition of Unsolicited and Solicited AE

An unsolicited adverse event is an adverse event that is communicated by a participant or their legal representative who has signed the informed consent. Unsolicited AEs include serious and non-serious AEs.

Potential unsolicited AEs may be medically attended (ie, symptoms or illnesses requiring a hospitalization, or emergency room visit, or visit to/by a health care provider). The participant or their legal representative will be instructed to contact the site as soon as possible to report medically attended event(s), as well as any events that, though not medically attended, are of concern. Detailed information about reported unsolicited AEs will be collected by qualified site personnel and documented in the participant's records.

Unsolicited AEs that are not medically attended nor perceived as a concern by the participant or their legal representative will be collected by interview with the participant/legal representative and by review of available medical records at the next visit.

Solicited AEs are predefined local and systemic events for which the participant is specifically questioned and/or instructed to report.

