3. STUDY OBJECTIVES AND ESTIMANDS

3.1. Primary Objectives and Estimands: Pharmacokinetics and Safety

Pharmacokinetic Objective(s)	
To evaluate the pharmacokinetics (PK) of brensocatic in participants with cystic fibrosis (CF) following once daily (QD) oral administration of study drug	
Population	Participants with CF defined by the inclusion and exclusion criteria of the CSP who received brensocatic
Treatment Regimen	1 tablet QD of brensocatic (actual treatment)
Endpoints	C_{max} , t_{max} , AUC_{0-24} , and $t_{1/2}$ on Day 1 and Day 28
Population Level Summary	Mean brensocatic dose levels for C_{max} , AUC_{0-24} , and $t_{1/2}$, median for t_{max}
Intercurrent Event (ICE)	
 Early discontinuation from brensocatic for any reason Not on stable cystic fibrosis transmembrane conductance regulator (CFTR) modulators for participants on modulators
Strategy	
For the first ICE, the While-On-Treatment strategy (including up to Day 35 follow-up period) will be applied.
 
For the second ICE, the Treatment Policy strategy will be used.

C_{max} = maximum plasma concentration, t_{max} = time to maximum plasma concentration, AUC_{0-24} = area under the concentration-time curve from time 0 to 24 hours post-dose, $t_{1/2}$ = elimination half-life.

Safety Objective(s)	
To evaluate the safety of brensocatic compared to placebo in participants with CF	
Population	Participants with CF defined by the inclusion and exclusion criteria of the CSP
Treatment Regimen	1 tablet QD of brensocatic or placebo (actual treatment)
Endpoints	Participant reported treatment-emergent adverse event (TEAE) and type of TEAE
Population Level Summary	Number and percentage of participants with each type of TEAEs and number of TEAEs
ICE	
 Early discontinuation from randomized investigational product (IP) for any reason
Strategy	The While-On-Treatment strategy (including the 28-days follow-up) will be applied.

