10.2. Adverse Events

The second primary endpoint is the incidence of TEAEs. The strategies as outlined in [Section 3.1](#) and [Section 7.2](#) will be applied for ICEs.

The AE verbatim descriptions (Investigator terms from the eCRF) will be coded by standardized medical terminology using MedDRA. AEs will be coded to primary SOC and PT using the most recent MedDRA version.

A TEAE is defined as any AE that occurs on or after the first dose of IP and within 28 days after the last dose of IP. AEs that occur between the time the participant had signed the Informed Consent Form for the study and before the participant receives the first dose of IP on Study Day 1 will be summarized as medical history and not as an AE unless the event meets the definition of a serious adverse event (SAE).

Where AE start dates are missing or partially missing, AEs will be assumed to be treatment-emergent, unless the partial start date or the AE end date gives clear evidence that the AE started before the first administration of IP.

Table 4: TEAE Assignment in Case of Missing AE Start Date Elements

Missing elements of AE start	Rule (IP start = first dose of IP)	Classification
Regardless of any missing information for AE start: AE end date < IP start date		non-TEAE
Otherwise (i.e., if AE end date \geq IP start date)		
- day/month/year	all AEs	TEAE
- day and month	AE start year \geq IP start year	TEAE
	AE start year < IP start year	non-TEAE
- day	AE start month/year \geq IP start month/year	TEAE
	AE start month/year < IP start month/year	non-TEAE

Duration of AEs will be calculated in days as:

$$\text{AE end date} - \text{AE start date} + 1.$$

If the start or the end date of the AE is not complete, the duration cannot be calculated and will be missing.

Summaries that are displayed by SOC and PT or by PT and will be ordered by descending order of total number of participants of SOC and PT within each SOC or by descending order of total number of participants of PT. SOC and PTs with the same number of participants will further be ordered by number of events. In the case of the same number of events, SOC and PTs will be ordered alphabetically.

Summary tables will present number and percentage of participants with TEAEs and number of events.

The following tables will be presented:

- Overall summary of TEAEs, specifically participants with at least one:
 - TEAE,
 - TEAE related to IP,
 - serious TEAE,
 - serious TEAE related to IP,
 - TEAE resulting in death,

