10.3. Clinical Laboratory Evaluations

For the general layout of the tables see [Section 7.1](#).

Continuous laboratory tests (hematology, clinical chemistry, and coagulation) will be summarized using descriptive statistics at scheduled visits (Screening, baseline, and EoT [Day 28 or Early Discontinuation]) for observed values and changes from baseline.

Shift tables (i.e., low-normal-high at baseline versus low-normal-high at EoT in a 3-by-3 contingency table) will be provided to assess changes in laboratory values from baseline to last visit with respect to the reference range. Reference ranges established by the central laboratory will be used to determine the categories. Values below the lower limit (LL) of the reference range will be classified as “low”. Values above the upper limit (UL) of the reference range will be classified as “high”. Values within the reference range will be classified as “normal”.

Clinical laboratory results will be provided in participant listings.

Participants experiencing alanine aminotransferase or aspartate aminotransferase $\geq 3 \times$ upper limit of normal (ULN) and total bilirubin $> 2 \times$ ULN according to Hy's Law will be listed.

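### SAP 7.2 cuts safety data at discontinuation of study drug, against the 28-day TEAE window in SAP 3.1, SAP 10.2 and protocol 10.3.1; read literally, it drops events that start after an early stop

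*SAP*

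**What the plan says.** The SAP gives two rules for safety data after an early stop.

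**Rule A: keep 28 days.** For the safety estimand, SAP 3.1 says: "The While-On-Treatment strategy (including the 28-days follow-up) will be applied". SAP 10.2 counts as treatment-emergent any AE from first dose and "within 28 days after the last dose of IP". Protocol 10.3.1 uses the same limit, "within 28 days after the last dose of study IMP".

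**Rule B: cut at the stop.** In the SAP 7.2 table, the Safety row handles early discontinuation as follows: "data collected prior to the occurrence of the ICE, i.e., to discontinuation of IP, will be included in the analysis". The text below the table repeats the cut and names safety: "data collected after discontinuation of IP will be excluded from the derivation of PK parameters and from statistical analysis for PK, safety". Neither place mentions a 28-day extension.

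Other provisions bear on the choice:

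- SAP 10.2 calls TEAE incidence the second primary endpoint and applies the strategies of both 3.1 and 7.2 to it.
- Protocol 9.4.5.1 includes AEs collected at early discontinuation in the AE tables.
- SAP 10.3 summarizes laboratory values at "EoT [Day 28 or Early Discontinuation"], so it expects to use measurements taken at that visit.
- Protocol 7.1 limits who is followed after stopping: "Participants who discontinue the study drug for any reason may not continue in the study unless discontinuation was due to an AE". Everyone else who stops is asked to attend an Early Discontinuation Visit.
- SAP 7.2 leaves the While-On-Treatment cut-off to the Blind Data Review Meeting.

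**The concern.** For anyone who stops early, Rules A and B cannot both be followed, and the section defining the TEAE analysis calls on both. Two programmers working from the same SAP could produce different TEAE tables, each with a textual basis.

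The choice matters because no hypothesis is tested, so the descriptive TEAE tables are the safety result. Post-stop data will come mainly from participants who stopped because of an AE, since protocol 7.1 lets only them continue. New events in these participants are of clear safety interest, and Rule B would leave them out of the summaries. Rule B also leaves it unclear whether the later course of an AE that began before the stop, such as becoming serious or fatal, counts as data collected after discontinuation.

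The same drafting gap affects other endpoints. SAP 3.1 to 3.3 extend While-On-Treatment to the Day 35 follow-up for PK, PD and CFQ-R, and 7.2 gives none of them an extension.

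**Working it through.** **1. The plan's own safety figures.** SAP 4.2 gives the chance of seeing at least one AE in a dose group. The formula is 1 − (1 − p)^N.

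- p = 15%: N = 10 gives 80.3% (stated 80%); N = 7 gives 67.9% (stated 68%).
- p = 21%: N = 10 gives 90.5% (stated 90%); N = 7 gives 80.8% (stated 80%).

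These reproduce. The contradiction does not depend on them, but they give a scale.

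**2. Does anything rank the two rules?** SAP 2 lets the SAP prevail over the protocol, but both rules are in the SAP. SAP 13 reports no change from the protocol-specified analyses, which favours Rule A, because Rule B would depart from protocol 10.3.1 and 9.4.5.1. That is an inference and not a stated order of precedence.

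**3. Window removed per early stopper under Rule B.** With the last dose on Day k, the TEAE window is k + 28 days, of which 28 are removed. The share is 28/(k + 28).

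- Day 7: 28/35 = 80%
- Day 14: 28/42 = 67%
- Day 21: 28/49 = 57%
- Day 27: 28/55 = 51%

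These are shares of calendar window, not of events. For someone who leaves at the Early Discontinuation Visit, much of that window may never be observed. Completers lose nothing, because the intercurrent event is early discontinuation.

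**4. Weight of one lost participant in a table row.** Active arm of 7: 1/7 = 14.3 points. Pooled placebo: 1/6 = 16.7 points with the 65 mg cohort, 1/4 = 25 points without it.

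**5. Which rows can move.** If an on-treatment AE caused the stop, it began before the cut, so that participant is already in the any-TEAE row under either rule. The difference appears where a new type of event starts after the stop: a particular SOC or preferred term, a serious or fatal event, or an AESI.

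**6. Illustration of detection.** The assumptions here are not in the documents: constant hazard giving 15% over 56 days, so h = −ln(0.85)/56; an arm of 7; m participants stopping on Day 14; and full 28-day follow-up. The probability of at least one event is 1 − exp(−h × D), where D is total observed days.

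- m = 0: D = 7 × 56 = 392 under both rules; 67.9%.
- m = 1: Rule A, D = 6 × 56 + 42 = 378, 66.6%; Rule B, D = 6 × 56 + 14 = 350, 63.8%.
- m = 2: Rule A, D = 5 × 56 + 84 = 364, 65.2%; Rule B, D = 5 × 56 + 28 = 308, 59.1%.
- m = 3: Rule A, D = 4 × 56 + 126 = 350, 63.8%; Rule B, D = 4 × 56 + 42 = 266, 53.8%.

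The loss is about 3 points with one stopper and 10 with three.

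**The case against.** The best defence is that 7.2 was never meant to override the rest. It presents its table as an overview and refers back to Section 3, where the 28-day extension is written. SAP 10.2 has the operative TEAE definition, the protocol agrees with it, and SAP 10.3 plainly expects Early Discontinuation laboratory values. On that reading 7.2 is shorthand and nothing is lost. All AEs are listed in any case, deaths have their own listing, and the cut-off is settled at a blinded, documented meeting before lock.

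Much of this stands. The loss is conditional on a literal reading, and it affects summaries, not listings. It does not remove the conflict: the closing paragraph of 7.2 names safety expressly, and 10.2 invokes 7.2 by number. A cut-off decided at a meeting is no substitute for a pre-specified rule, and 7.2 allows those decisions to be revised, with a rationale, after unblinding.

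A reader might infer more than the documents support:

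- *That incidence would be biased downward mainly in the active arms.* The documents give no expected imbalance in stopping. Protocol 2.3.3 reports a similar overall safety profile across groups in the earlier trials, with no discontinuation from the skin events.
- *That most of an early stopper's safety information is lost.* The 51% to 80% figures are calendar time.
- *That overall arm incidence moves by 14 points or more.* Step 5 of the working limits that to specific rows.
- *That the 65 mg decision is affected.* SAP 2 leaves the scope of the Safety Review Committee's analyses to its charter, and nothing shows that 7.2 governs it.

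**Conclusion.** The contradiction is real and concerns a primary endpoint. SAP 7.2 as written is incompatible with SAP 3.1, SAP 10.2, protocol 10.3.1 and protocol 9.4.5.1, and with the use of Early Discontinuation laboratory values in SAP 10.3. It needs correcting even though the weight of the text favours the 28-day window.

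The numerical consequence is uncertain and may be nil. It requires that 7.2 is applied literally, that someone stops early, and that a new event starts after the stop and is recorded. Given all three, one participant shifts a specific row by 14 points in an arm of 7. The documents do not give the number or timing of early stops, so no expected size and no direction between arms can be stated. The case for the change rests on having one pre-specified rule.

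**What to change.** Before database lock, edit SAP 7.2 as follows:

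- **Safety row and closing paragraph.** State that all safety data from first dose to 28 days after the last dose are analysed whether or not study drug was stopped early, and that Early Discontinuation assessments are included. Remove safety from the list of analyses cut at discontinuation.
- **PK and PD rows, and CFQ-R within the efficacy row.** Carry over the Day 35 extension from 3.1 to 3.3 and say what it means for someone who stops before Day 28. PK needs particular care: the protocol's sampling schedule times the Day 35 sample at 168 hours after the Day 28 dose, so the SAP must say whether the limit is the calendar day or an interval from the last dose actually taken. Spirometry and microbiology have no such extension in 3.3, so CFQ-R needs its own sentence.
- **Blind Data Review Meeting.** Limit its role for safety to applying the stated window and documenting the dates.

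The cost is a short text revision to one SAP section. No new data and no protocol amendment are needed, because the safety change brings the SAP back to the protocol's own definition.

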7.3. Multiple Comparisons and Multiplicity

There is no formal hypothesis-testing in this study, and no inferential conclusions will be drawn from the study results. Therefore, corrections for multiple testing are not applicable.

8. STUDY POPULATION SUMMARIES

For the general layout of the tables see [Section 7.1](#).

The study population summaries will be reported for the PK Analysis Set unless otherwise stated and will be repeated for the Safety Analysis Set. If both analysis sets comprise the same participants, only the table for the PK Analysis Set will be produced.

8.1. Subject Disposition

For participants screened, the number of participants who are screened and the number of participants who failed screening, the reasons for screen failure and whether it is related to corona virus disease 2019 (COVID-19) will be summarized.

Subject disposition will be summarized to present the number and percentage of participants (overall and within randomization strata CFTR modulator / non-modulator)

- randomized,
- randomized and treated,
- who completed/discontinued from IP and the study with reason for discontinuation.

Percentages will be based on the Screened Analysis Set. Percentages of reasons for discontinuation of the study/IP will be based on the participants who discontinued the study/IP.

Number and percentage of participants included in each of the analysis sets described in [Section 6](#) will also be presented (overall and within randomization strata CFTR modulator / non-modulator).

Reasons for exclusion from analysis sets will be summarized using number and percentage of participants. The percentages will be based on the Screened or Randomized Analysis Sets.

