### **5.4. Screen Failures**

Screen failures are defined as participants who consent to participate in the clinical study but are not subsequently randomized to receive study drug. A minimal set of screen failure information is required to ensure transparent reporting of screen failure participants to meet the Consolidated Standards of Reporting Trials publishing requirements and to respond to queries from regulatory authorities. Minimal information includes demography, screen failure details, eligibility criteria, and any SAE.

Individuals who do not meet the criteria for participation in this study (screen failure) may be rescreened after consultation with the study Medical Monitor. Participants who meet all inclusion criteria but fail screening due to active PE or ongoing standard periodontal care can be rescreened up to 2 times with the Sponsor's Medical Director approval. If a participant is approved for rescreening, the Medical Director will determine whether some or all of the screening assessments must be repeated.

NOTE: Rescreened participants should be assigned a new participant number ("subject ID") by the IWRS system for every screening/rescreening event.
--

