6. ANALYSIS SETS

6.1. Screened Analysis Set

The Screened Analysis Set comprises all participants who provide written informed consent.

Technical Note: Participants with non-missing date of informed consent will be included.

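### SAP 8.1 divides treated, completed and discontinued counts by everyone who consented, so screen failures lower the overall completion and all-cause discontinuation percentages

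*SAP*

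**What the plan says.** SAP 8.1 (Subject Disposition) asks for number and percentage, overall and within the CFTR modulator and non-modulator strata, of participants randomized, participants randomized and treated, and those "who completed/discontinued from IP and the study with reason for discontinuation". The base follows: "Percentages will be based on the Screened Analysis Set". One exception comes next: "Percentages of reasons for discontinuation of the study/IP will be based on the participants who discontinued the study/IP". No other base is given for completion or discontinuation.

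SAP 6.1 defines the base: "The Screened Analysis Set comprises all participants who provide written informed consent". Its technical note selects on the consent date: "Participants with non-missing date of informed consent will be included".

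Protocol 5.4 defines the people in that set who go no further: "Screen failures are defined as participants who consent to participate in the clinical study but are not subsequently randomized to receive study drug". It also states that "Rescreened participants should be assigned a new participant number", at every screening or rescreening event. Protocol 10.1.5 requires a new consent form at rescreening.

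SAP 6.2 defines a Randomized Analysis Set. SAP 8.1 names it only as a possible base for reasons for exclusion from analysis sets.

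**The concern.** A percentage completing or discontinuing treatment is useful when its denominator holds the people who could have done either. Screen failures could not, because they were never randomized. Putting them in the denominator mixes screening yield with retention, and both the completion and the discontinuation figure fall as more people fail screening. A trial with no dropouts at all would show completion below 100%.

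Two further gaps sit beside this. The disposition table is to be shown within randomization strata, and SAP 7.1 lays tables out by treatment group, but unrandomized people have no assigned arm and do not appear in the randomization file. The SAP has no rule for where they go. Also, a rescreened person can hold several IDs, each with its own consent date, and the SAP has no rule for linking them.

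What is at stake is how the all-cause discontinuation and completion percentages read in the study report. Protocol 9.4.5 commits to summarizing withdrawals and their primary reasons, and SAP 8.1 is where that is done.

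**Working it through.** The documents state no screen-failure, rescreen or discontinuation rate, so there is no planned figure to reproduce. The planned numbers randomized do check: 3 × 7 + 4 = 25, and 25 + 7 + 2 = 34 with the 65 mg cohort.

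**Inputs from the documents**
- N randomized: about 25, or about 34 with the fourth cohort (SAP 4.1).
- Denominator: everyone with a consent date (SAP 8.1 with 6.1).
- Rescreening: up to 2 times for active exacerbation or ongoing periodontal care (Protocol 5.4), so up to 3 IDs for one such person.

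**Assumed inputs, for illustration only**
- d discontinued: 3 of 25, or 4 of 34.
- f, the share of screened persons who fail screening: 10%, 30% or 50%.
- r, extra IDs from rescreening that are not linked: 0 or 5.

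**Formulas**
- Persons screened: S = N / (1 − f), rounded to a whole person.
- Percentage under SAP 8.1: d / (S + r) discontinued and (N − d) / (S + r) completed.
- Percentage of randomized participants: d / N and (N − d) / N.

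With r = 0, the SAP 8.1 figure is the randomized-based figure multiplied by about (1 − f). The direction therefore does not depend on the assumed counts: any f above zero lowers both percentages.

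**N = 25, d = 3.** On the randomized base, 3/25 = 12.0% discontinued and 22/25 = 88.0% completed.

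| f | r | Denominator | Discontinued | Completed |
|---|---|---|---|---|
| 10% | 0 | 28 | 10.7% | 78.6% |
| 30% | 0 | 36 | 8.3% | 61.1% |
| 50% | 0 | 50 | 6.0% | 44.0% |
| 10% | 5 | 33 | 9.1% | 66.7% |
| 30% | 5 | 41 | 7.3% | 53.7% |
| 50% | 5 | 55 | 5.5% | 40.0% |

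**N = 34, d = 4.** On the randomized base, 4/34 = 11.8% and 30/34 = 88.2%. With r = 0 and f of 10%, 30% and 50%, the denominators are 38, 49 and 68. Discontinuation reads 10.5%, 8.2% and 5.9%, and completion 78.9%, 61.2% and 44.1%.

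**No dropouts, N = 25, f = 30%, r = 0.** Completion reads 25/36 = 69.4% instead of 100%.

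**Whether another section supplies a different base.** SAP 8 defaults to the PK Analysis Set, but only where nothing else is stated, and 8.1 states something else. SAP 7.1 requires footnotes naming the percentage base, which discloses the choice without changing it. SAP 7.1 also lets the randomization file prevail where it and the eCRF disagree on stratum. That rule settles conflicts but does not cover people who are absent from the file.

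**The case against.** The strongest reply is that little depends on this table, and most of that reply stands.

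- **Tolerability is covered elsewhere.** A reader might infer that a headline tolerability figure is being understated. The documents do not support that. The primary safety endpoint is the frequency of TEAEs. SAP 10.2 tabulates TEAEs leading to withdrawal from study or IP, both in the overall summary and by SOC and PT, on the Safety Analysis Set of treated participants. SAP 10.1.1 also reports bands of treatment duration on the Safety and PK sets. All-cause discontinuation, however, is summarized only in 8.1.
- **The base is visible.** Counts appear beside percentages and footnotes name the base, so a reader can recompute the rate. The percentage is a poor choice of base rather than an undetectable error.
- **Arm columns may be unaffected.** A reader might infer that by-arm percentages are diluted, or have no valid denominator. Neither follows. SAP 7.1 sets the column N as the participants of that treatment group within the analysis set, so an arm column could hold only randomized people, with dilution confined to the overall figures. The SAP does not say that this is how 8.1 should be applied, so what remains is a missing rule.
- **Double counting is not stated.** SAP 6.1 counts participants. Repeat counting would arise only if programming treats each ID as a separate person. The table shells and programming specifications are not among the documents, so this is a risk and not a finding.
- **The magnitudes are illustrative.** At 10% screen failure the change from 12.0% to 10.7% is small.

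None of these points gives a reason to keep screen failures in the denominator for completing or discontinuing IP.

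**Conclusion.** The point holds for the overall percentages. Followed as written, SAP 8.1 understates the treated, completed and all-cause discontinued percentages relative to randomized participants whenever anyone fails screening. Under the assumed 3 of 25 discontinuing, 12% reads between 10.7% and 6.0%, and 88% completion between 78.6% and 44.0%, for screen failure of 10% to 50% with no repeat counting. The direction follows from the text; the size rests on a screening ratio that the documents do not give.

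Two lesser points go with it: the placement of unrandomized people in arm and stratum columns is unspecified, and rescreened people could be counted more than once if their IDs are not linked.

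The reach is limited to descriptive reporting of disposition. Percentages by reason for discontinuation have their own base and are unaffected. No PK or TEAE estimate changes.

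**What to change.** Replace the single denominator sentence in SAP 8.1 with separate bases:

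- Screen-failure and randomized percentages: the Screened Analysis Set, overall only, with each person counted once by linking rescreening IDs.
- Randomized-and-treated percentages, and completion and discontinuation of the study: the Randomized Analysis Set, by arm, by stratum and overall.
- Completion and discontinuation of IP: the Randomized Analysis Set or randomized-and-treated participants, with the choice stated, by arm, by stratum and overall.
- Reasons for discontinuation: unchanged.

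Add to SAP 6.1 that a rescreened person contributes once to the Screened Analysis Set.

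The cost is a short text change in the SAP and new denominators in one table shell. The Randomized Analysis Set is already defined, and neither data collection nor any estimand changes. The edit should be made before database lock.
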